8.9. Concomitant Medications or Therapies

Concomitant therapies and medications, including medications that are taken on an as needed basis and occasional therapies, will be monitored during the study. Details of prohibited medications may be found in Section 5.7 of the study protocol. All concomitant medications will be coded using the WHO Drug.

The incidence of concomitant therapies and medications will be summarized using descriptive statistics by therapeutic class category, preferred base name and preferred term. Patients are counted only once in each therapeutic class, once in each preferred base name, and only once in each preferred term category. Concomitant therapies and medications will include all medications taken after the first administration of the IMP up to the end of study as defined in the study protocol.

In order to determine whether a medication is concomitant, partial start dates with missing day and/or month will be imputed with the first day of the month/first month of the year, respectively and partial end dates with missing day and/or month will be imputed with the 28th day of the month/last month of the year respectively. Imputed dates will be used for calculations only, actual dates will be listed.

Prohibited medications that are associated with QTc prolongation are listed in Appendix H, Table 11, of the study protocol. Any incidence of these prohibited medications will be listed separately.

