2.4. Sample Size and Power Considerations

The initial sample size estimation of approximately 185 patients randomized to TEV-50717 versus placebo in a 2:1 ratio (approximately 124 in the TEV-50717 group; approximately 61 in the placebo group) is the sample size required to obtain a statistically significant result in the primary analysis based on a 1-sided test for mean difference at a significance level of $\alpha=0.025$ with a power of approximately 90%, assuming a mean difference of 1.8 and a standard deviation (SD) of 3.5 in each treatment group.

Based on Protocol Amendment 05, the initial planned sample size has been reduced to approximately 65 patients randomized to TEV-50717 versus placebo in a 2:1 ratio (approximately 43 in the TEV-50717 group; approximately 22 in the placebo group).

The initial assumptions regarding the mean difference and SD are based on the change from baseline to month 6 in patients treated with trihexyphenidyl reported by [Battini et al \(2014\)](#), assuming an effect size of 55% for TEV-50717 versus placebo. The effect size of 55% was assumed based on the observed effect sizes of TEV-50717 in the pivotal studies in Huntington's disease and tardive dyskinesia. In the current study, these assumptions correspond to a mean difference of 2.0 in MD-CRS part II total score and an SD of 3.5 in each treatment group.

The rate of missing not at random (MNAR) data for the primary analysis is expected to be 10%. MNAR data will be imputed in a conservative manner as if they were obtained from patients in the placebo treatment group, regardless of the actual treatment group. As a result, the mean difference is expected to be reduced from 2.0 to 1.8 in the primary analysis. The impact of the missing data imputation on the SD is negligible.

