4.4. Study Days and Visits

Study days will be numbered relative to the baseline visit date. Day 1 is defined as the date of the baseline visit, and the first dose of the IMP will be taken the next morning (day 2). Days will be numbered relative to baseline (ie, ..., -2, -1, 1, 2, ...; day -1 being the day before the baseline visit).

For efficacy and safety by-visit analyses, data collected at post-baseline scheduled visits will be included using their scheduled visit.

Data collected at early termination and unscheduled visits will be included and assigned to a visit window as described below.

Table 2: Visit Windows for Early Termination Visit for Efficacy Assessments

Assessment ^a	Study Day Window	Scheduled Day	Scheduled Visit/Week
MD-CRS	Day 2 - 73	Day 63	Week 9
	Day 74 - 94	Day 84	Week 12
	Day 95 - EOT	Day 105	Week 15
	≥Day after EOT	Day 112	Week 16
CaGI-I, CGI-S, PGI-I	Day 2 - 35	Day 21	Week 3
	Day 36 - 53	Day 49	Week 7
	Day 54 - 73	Day 63	Week 9
	Day 74 - 94	Day 84	Week 12
	Day 95 - EOT	Day 105	Week 15
	≥Day after EOT	Day 112	Week 16
CGI-I	Day 2 - 10	Day 7	Week 1
	Day 11 - 17	Day 14	Week 2
	Day 18 – 24	Day 21	Week 3
	Day 25 - 31	Day 28	Week 4
	Day 32 - 38	Day 35	Week 5
	Day 39 - 45	Day 42	Week 6
	Day 46 - 53	Day 49	Week 7
	Day 54 - 73	Day 63	Week 9
	Day 74 - 94	Day 84	Week 12
	Day 95 - EOT	Day 105	Week 15
	≥Day after EOT	Day 112	Week 16
PEDI-CAT, PedsQL	Day 2 – EOT	Day 105	Week 15

Assessment ^a	Study Day Window	Scheduled Day	Scheduled Visit/Week
UHDRS-TMS, UHDRS-TMC, UHDRS-TMD	Day 2 - 73	Day 63	Week 9
	Day 74 - 94	Day 84	Week 12
	≥Day 95 - EOT	Day 105	Week 15

^a CaGI-I=Caregiver Global Impression of Improvement; CGI-I=Clinical Global Impression of Improvement; CGI-S=Clinical Global Impression of Severity; PGI-I=Patient Global Impression of Improvement; UHDRS-TMS=Unified Huntington’s Disease Rating Scale-Total Motor Score; UHDRS-TMC=Unified Huntington’s Disease Rating Scale-Total Maximal Chorea; UHDRS-TMD=Unified Huntington’s Disease Rating Scale-Total Maximal Dystonia; EOT=end of treatment

Table 3: Visit Windows for Early Termination Visit for Safety Assessments

Assessment ^a	Study Day Window	Scheduled day	Scheduled Visit/Week
Vital signs, Weight, C-SSRS, ESRS, CBCL- Syndrome Scale, ESS	Day 2 - 35	Day 21	Week 3
	Day 36 - 53	Day 49	Week 7
	Day 54 - 74	Day 63	Week 9
	Day 75 - 94	Day 84	Week 12
	Day 95 – EOT	Day 105	Week 15
	≥Day after EOT	Day 112	Week 16
ECG	Day 2 - 35	Day 21	Week 3
	Day 36 - 67	Day 49	Week 7
	Day 68 – EOT	Day 105	Week 15

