5.6. Prior Therapy and Medication

Any prior or concomitant medication a patient has had within 3 months prior to baseline and up to the end of study, including follow up, will be recorded on the CRF. Generic or trade name, indication, dose, and start and end dates of the administered medication will be recorded. The sponsor will encode all medication according to the WHO drug dictionary.

The incidence of prior therapies and medications will be summarized using descriptive statistics by therapeutic class, preferred base name and preferred term. Patients are counted only once in each therapeutic class category, and only once in each preferred term category. Prior therapies and medications will include all medications taken and therapies administered before the first day of IMP administration.

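### A missing medication end day is set to the 28th, so when the first dose falls on the 29th to 31st a drug taken on or after it can be counted as prior only

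*SAP*

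**What the plan says.** SAP section 8.9 defines the category by timing: "Concomitant therapies and medications will include all medications taken after the first administration of the IMP up to the end of study". Section 5.6 gives its counterpart: "Prior therapies and medications will include all medications taken and therapies administered before the first day of IMP administration".

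For incomplete dates, section 8.9 gives its purpose as settling whether a drug counts as concomitant. A missing start day becomes the 1st, and a missing start month becomes January. For ends, "partial end dates with missing day and/or month will be imputed with the 28th day of the month/last month of the year respectively". It adds: "Imputed dates will be used for calculations only, actual dates will be listed".

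Under section 4.4 the first dose is taken the morning after the baseline visit, on day 2. Nothing in the SAP keeps that morning off the 29th, 30th or 31st. Nor does any section cap or override the end-date rule, for example when the end falls in the month of the first dose or when the imputed end precedes a known start.

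**The concern.** A convention for incomplete dates in a safety summary usually leans towards inclusion: if a drug could have been taken during treatment, it is counted. Three of the four choices in section 8.9 do this. The missing start day, missing start month and missing end month all go to the extreme that makes overlap with treatment most likely. The missing end day does not, because the 28th is one to three days short of month end in eleven months of the year, and one day short in a leap-year February.

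The shortfall matters only when the first dose falls after the 28th. Suppose the first dose is on 30 March and a drug's end is recorded only as March. The imputed end is 28 March, so the drug is treated as finished before dosing, although it may have been taken on the 30th or 31st.

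A second symptom needs no assumption about the true stop day. A drug with a full start date of 30 March and an end recorded only as March gets an end two days before its start. If the first dose was on 29 March, the drug is certainly concomitant, yet its imputed end says otherwise. The SAP does not say which date then governs.

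At stake is the accuracy of the concomitant-medication incidence tables.

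**Working it through.** The SAP gives no figure on this point, so there is none to reproduce. The check follows the date rule through the calendar.

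**Inputs.** Imputed end day 28, with December if the month is missing (section 8.9); concomitant means taken after the first dose (section 8.9); the first dose can fall on any date (section 4.4); about 65 patients (section 2.4: "the initial planned sample size has been reduced to approximately 65 patients randomized to TEV-50717 versus placebo in a 2:1 ratio"). Assumptions not in the SAP: first-dose dates evenly spread over the calendar, true stop days uniform over the month, and a stop on the day of first dose counted as concomitant.

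**1. First-dose dates exposed.** The imputed end precedes a first dose in the same month when the first dose is after the 28th.
- Non-leap year: seven 31-day months × 3 + four 30-day months × 2 = 29 of 365 (7.9%).
- Leap year: 30 of 366 (8.2%).
- 2019 to 2022: 3 × 29 + 30 = 117 of 1461 (8.0%).
- Patients with such a first dose: 0.080 × 65 = 5.2.

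**2. Year-only end dates.** The imputed end is 28 December, so only first doses on 29 to 31 December are exposed: 3 dates a year.

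**3. How often the result is wrong.** For exposed first-dose dates in a non-leap year:
- Stop days on or after the first dose: 7 × (3 + 2 + 1) + 4 × (2 + 1) = 54.
- All possible stop days: 7 × (3 × 31) + 4 × (2 × 30) = 651 + 240 = 891.
- Truly misclassified: 54/891 = 6.1%. Correctly classed as prior: 837/891 = 93.9%.

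**4. Share of all same-month concomitant use missed.** Over every first-dose date in a non-leap year, the pairs with a stop on or after first dose number 7 × 496 + 4 × 465 + 406 = 5738. The rule misses 54/5738 = 0.9%.

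**5. Expected count.** Let k be the mean number of drugs per exposed patient whose end is known only to the month of first dose. The expected number misclassified is 5.2 × k × 0.061. The SAP gives no basis for k. For k from 0.1 to 1, the result runs from about 0.03 to 0.3 drugs in the whole trial.

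**6. Strict reading.** If a stop on the day of first dose does not count as concomitant, first doses on the 28th are exposed too: 29 + 12 = 41 of 365 dates. The misclassified share is then 54 of (7 × 4 × 31 + 4 × 3 × 30 + 28 = 1256), or 4.3%. The order of size is unchanged.

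**7. After the change.** With the last calendar day, the imputed end is never before a first dose in the same month: 0 of 365 dates.

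**The case against.** The strongest reply is that this is a date convention valid in every month, feeding one descriptive table, and that the harmful combination is rare. It needs a first dose after the 28th, a drug ending that same month with the day unrecorded, and actual use on or after the first dose. Medication start and end dates are collected on the CRF (section 5.6), and contacts are weekly from week 1 (section 2.1), so a stop within days of the first dose should usually be dated. Actual dates are still listed. All of this stands and limits the size of the point. It does not make the rule right, because a listing does not correct a table.

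Several stronger readings are tempting, and the SAP does not support them:

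- **Every such drug is misclassified.** No. A drug is wrongly classed as prior only if it was really taken on or after the first dose.
- **About 5 patients are affected.** No. That is the expected number with an exposed first-dose date, before asking whether they have such a drug.
- **The rule errs only towards missing use.** No. For first doses on the 1st to 28th, it counts every same-month, day-missing drug as concomitant, including those stopped beforehand.
- **The per-protocol set is distorted.** A medication that was not permitted is a listed ground for exclusion in Table 1. However, section 3.4 decides exclusions case by case, before database lock and unblinding, and section 5.9 takes important deviations from the trial management system. Nothing ties either to the imputed flag.

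It is also fair to say that the SAP never states that it wants the latest possible end. That intention is inferred from the other three choices. A drug with a known start after first dose could reasonably be classed by its start, but the SAP leaves that to the programmer.

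**Conclusion.** The point holds as a minor defect. For first doses on the 29th to 31st, the end-day rule in section 8.9 always places a same-month end of unknown day before treatment, and it can produce an end before a known start. About 8% of calendar days are exposed, which is about 5 of 65 patients if first doses are evenly spread. About 6% of the drugs concerned would truly be misclassified if stop days are uniform. Both assumptions are illustrative, and the number of incomplete end dates is unknown, so no firm count can be given; it is likely to be below one drug. The consequence is confined to the descriptive concomitant-medication tables. No efficacy analysis, test or per-protocol decision is shown to depend on it.

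**What to change.** In section 8.9, replace the 28th with the last calendar day of the month, and use 31 December when the month is also missing. This completes the inclusive pattern of the other three choices and removes the end-before-start case for known starts in the same month. It costs a few words in the SAP and one end-of-month date function.

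The change is a trade-off. For the exposed first-dose dates, drugs that stopped before the first dose (837 of 891 stop-day combinations under the uniform assumption) will be counted as concomitant. The rule already accepts the same over-counting for first doses on the 1st to 28th, so the change makes the treatment consistent across the month, and the number of drugs involved is small.

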8.10. Children’s Columbia-Suicide Severity Rating Scale

The frequency and severity of suicidal ideation or behavior according to the children’s C-SSRS questionnaire will be presented for all patients aged ≥ 12 years by visit and by treatment group. A shift table to examine changes in children’s C-SSRS categories from baseline (using the lifetime version of the questions), compared to the worst (highest) category during the treatment period will be presented by treatment and overall.

Patients will be placed into categories for suicidal ideation and suicidal behavior based on their responses to various questions. The suicidal ideation categories will be determined by the following 5 questions.

Table 8: Suicidal Ideation Category

Type	Category
Suicidal Ideation	(0) None – if response is No to Questions 1 and 2 (1) Wish to be Dead – if response to Question 1 is Yes and responses to Question 2 is No. (2) Non-Specific Active Suicidal Thoughts – if response to Question 2 is Yes and response to Questions 3-5 are No. (3) Active Suicidal Ideation with Any Methods (Not Plan) without Intent to Act – if response to question 3 is Yes and response to questions 4 and 5 are No. (4) Active Suicidal Ideation with Some Intent to Act, without Specific Plan – if response to Question 4 is Yes and response to Question 5 is No. (5) Active Suicidal Ideation with Specific Plan and Intent – if response to Question 5 is Yes.

For suicidal behavior, the following categories will be used. The categories will be determined based on the response to the questions.

Table 9: Suicidal Behavior Category

Type	Category
Suicidal Behavior	
(6) Preparatory Acts or Behavior – if response to Preparatory Acts and Behavior is Yes and responses to Actual Attempt, Interrupted Attempt, Aborted Attempt, and Completed Suicide are No
 
(7) Aborted Attempt – if response to Aborted Attempt is Yes and responses to Actual Attempt, Interrupted Attempt, and Completed Suicide are No.
 
(8) Interrupted Attempt – if response to Interrupted Attempt is Yes and response to Actual Attempt, and Completed Suicide are No.
 
(9) Actual Attempt – if response to Actual Attempt is Yes and Completed Suicide is No.
 
(10) Completed Suicide - if response to Completed Suicide is Yes
 
(0) None – if responses to all the above questions are No.

Suicidal ideation or behavior will be derived as the highest suicidal ideation or behavior score at the visit. Score of 0 represent “No Suicidal Ideation/Behavior”.

The frequency and percentage of suicidal ideation, suicidal behavior, suicidal ideation or behavior, and self-injurious behavior without suicidal intent will be summarized by treatment and overall, and visit.

8.11. Child Behavior Checklist for Ages 6-18 (CBCL)

The CBCL assesses behavioral and emotional status in children ages 6 through 18 years of age as reported by the parent/caregiver (Achenbach and Ruffle 2000; Achenbach 2005). The full CBCL has 2 parts, a Competence Scale (Parts I to VII) and a Syndrome Scale (behavioral items).

8.11.1. Competence Scale

The Competence Scale (Parts I to VII) assesses various activities, interpersonal relationships, and academic performance. Competence assessment will be performed at screening and week 15/ET.

The competence scale is divided into 3 subscales – see [Table 10](#).

Table 10: CBCL Competence Scale

Activities	Social	School
I.A. number of sports	III.A. number of organizations	VII.1. Mean performance
I.B. Mean part/skills	III.B. Mean Participation	VII.2. Special class
II.A. number of activities	V.1 number of friends	VII.3. Repeated grade
II.B. Mean part/skills	V.2 Frequency of contact	VII.4. School problems
IV.A. number of jobs	VI.A. Behavior with others	
IV.B. Mean job quality	VI.B. Behavior alone	

Total score and change from baseline for each subscale separately and a total score and change from baseline for all items will be summarized for each time point using descriptive statistics for continuous variables. Total scores are rounded to nearest 0.5.

Scores per item are calculated as follows in [Table 11](#):

Table 11: CBCL Competence Scale Scoring

Subscale	Item	Scoring
Activities	I.A. number of sports	count the number of sports
	I.B. Mean part/skills	mean of up to 6 rates, 2 for each sport activity. Where 'below average' or 'Less than average'=0, 'Average'=1, 'above average' or 'More than average'=2
	II.A. number of activities	count the number of activities.
	II.B. Mean part/skills	mean of up to 6 rates, 2 for each activity. Where 'below average' or 'Less than average'=0, 'Average'=1, 'above average' or 'More than average'=2
	IV.A. number of jobs	count the number of jobs
	IV.B. Mean job quality	mean of up to 3 rates, 1 for each job. Where: 'below average'=0, 'Average'=1, 'above average'=2.
Social	III.A. number of organizations	count the number of organizations.
	III.B. Mean Participation	mean of up to 3 rates, 1 for each organization. Where: 'Less active'=0, 'Average'=1, 'More active'=2.
	V.1 number of friends	None'=0, '1'=1, '2 or 3'=2, '4 or more'=3.
	V.2 Frequency of contact	'Less than 1'=0, '1 or 2'=1, '3 or more'=2.
	VI.A. Behavior with others	mean of items a-c. Where: 'Worse'=0, 'Average'=1, 'Better'=2.
	VI.B. Behavior alone	rate for item d. Where: 'Worse'=0, 'Average'=1, 'Better'=2.
School	VII.1. Mean performance	Mean of up to 7 performance items. Where 'failing'=0, 'below average'=1, 'average'=2, 'above average'=3.
	VII.2. Special class	'Yes'=0, 'No'=1'.
	VII.3. Repeated grade	'Yes'=0, 'No'=1'.
	VII.4. School problems	'Yes'=0, 'No'=1'.

Values of 'Do not know', 'Not applicable', or 'Has no brothers or sisters' will be ignored for mean calculations and logically skipped items will be imputed as 0 or none.

A subscale score is calculated as the sum of the item scores and the total score is calculated as the sum of the subscale scores. If one or more subscale scores are missing, the total score is not calculated.

If 1 item from activities and social subscales has a missing value, the mean of the other items of that subscale is substituted for that item. If more than 1 item is missing from either of these scales or any item is missing from the school scale, the respective scale is not to be scored.

Results will be listed.

8.11.2. Syndrome Scale

The Syndrome Scale comprises 113 questions related to problem behaviors. Syndrome assessment will be performed at screening, baseline, weeks 3, 7, 9, 12, 15/ET, 16/EOS.

For each item, the parent/caregiver will circle “0” if the item is not true of their child, “1” if the item is somewhat or sometimes true, and “2” if the item is very true or often true.

The Syndrome scale is divided into 8 subscales – see [Table 12](#).

Table 12: CBCL Syndrome Scale

Anxious / Depressed		Withdrawn / Depressed	Somatic Complaints	Social Problems	Thought Problems	
14.Cries 30.FearsSchool 32.Perfect 35.Worthless 50.Fearful 71.SelfConsc 112.Worries	29.Fears 31.FearDoBad 33.Unloved 45.Nervous 52.Guilty 91.ThinksSuicide	5.EnjoysLittle 42.RatherBeAlone 65.Won'tTalk 69.Secretive 75.Shy 102.LacksEnergy 103.Sad 111.Withdrawn	47.Nightmares 49.Constipated 51.Dizzy 54.Tired 56a-g.Physical Problems without known medical cause ^a	11.Dependent 12.Lonely 25.NotGetAlong 27.Jealous 34.OutToGet 36.Accidents 38.Teased 48.NotLiked 62.Clumsy 64.PreferYoung 79.SpeechProb	9.MindOff 40.HearsThings 58.PicksSkin 60.SexPartsM 70.SeesThings 83.StoresUp 85.StrangeIdeas 100.SleepProb	18.HarmsSelf 46.Twitches 59.SexPartsP 66.RepeatsActs 76.SleepsLess 84.StrangeBehav 92.SleepWalk
Rule-Breaking Behavior		Attention Problems	Aggressive Behavior		Other Problems	
2.Alcohol 28.BreaksRules 43.LiesCheats 67.RunAway 73.SexProbs 82.StealsOther 96.ThinksSex 101.Truant 106.Vandalism	26.LacksGuilt 39.BadFriends 63.PreferOlder 72.SetsFires 81.StealsHome 90.Swears 99.Tobacco 105.UsesDrugs	1.ActsYoung 4.FailsToFinish 8.Concentrate 10.SitStill 13.Confused 17.Daydreams 41.Impulsive 61.PoorSchool 78.Inattentive 80.Stares	3.Argues 19.DemAtten 21.DestroyOther 23.DisobeySchl 57.Attacks 86.Stubborn 88.Sulks 94.Teases 97.Threaten	16.Mean 20.DestroyOwn 22.DisobeyHome 37.Fights 68.Screams 87.MoodChang 89.Suspicious 95.Temper 104.Loud	6.BMOut 15.CruelAnimal 44.BiteNail 55.Overweight 74.ShowsOff 93.TalkMuch 107.WetsSelf 109.Whining 113.OtherProb ^b	7.Brags 24.NoEatWell 53.Overeat 56h.OtherPhys 77.SleepsMore 98.ThumbSuck 108.WetsBed 110.WishOppSex

^a Item 56 stands for “Physical Problems without known medical cause: other” and may not be filled in by the responder.

^b Similarly, item 113 that stands for “Any problems that were not listed above” may be missing, for the same reason.

Total score for each subscale separately, total score for all items, change from baseline for the total score for each subscale separately and change from baseline for total score for all items will be summarized for each time point using descriptive statistics for continuous variables.

Total score is calculated as the sum of item scores.

If more than 20 items have missing values, excluding items 56h and 113, which may be left blank by structure (see [Table 12](#) for details), then no scores will be provided. For calculating subscale scores, if one or more items, excluding items 56h and 113, are missing in a subscale, the subscale score will not be calculated.

Data will be listed.

In addition, individual plots will be provided.

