4.3.5.2. Other Missing Items in Rating Scales

Rules for handling missing items in efficacy and safety rating scales are presented in Section 6.4 (Unified Huntington’s Disease Rating Scale-Total Motor Score (UHDRS-TMS), Unified Huntington’s Disease Rating Scale-Total Maximal Chorea (UHDRS-TMC), Unified Huntington’s Disease Rating Scale-Total Maximal Dystonia (UHDRS-TMD), Pediatric Evaluation Disability Inventory-Computer Adapted Test (PEDI-CAT), Pediatric Quality of Life Inventory (PedsQL) and Patient Global Impression of Improvement (PGI-I)) and Section 8 (Columbia-Suicide Severity Rating Scale [C-SSRS], Child Behavior Checklist [CBCL], Extrapyrimal Symptom Rating Scale [ESRS] and Epworth Sleepiness Scale [ESS]).

Unless otherwise specified, only those observed data from the patients will be used in the statistical analyses, ie, no estimation of missing data.

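### The CBCL Syndrome total is not adjusted for 1 to 20 unanswered items, so each blank counts as 0 and can only lower that form's problem score

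*SAP*

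**What the plan says.** SAP Section 8.11.2 describes the scale and its coding: "The Syndrome Scale comprises 113 questions related to problem behaviors", scored 0, 1 or 2, and "the parent/caregiver will circle “0” if the item is not true of their child". Higher totals mean more problems.

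Three scoring rules follow in the same section:

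- **Total:** "Total score is calculated as the sum of item scores".
- **Upper limit on missing items:** no scores at all are given under the condition "If more than 20 items have missing values, excluding items 56h and 113".
- **Subscales:** "if one or more items, excluding items 56h and 113, are missing in a subscale, the subscale score will not be calculated".

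Nothing is said about how the total is formed when 1 to 20 items are missing. The general default in Section 4.3.5.2 then applies: "Unless otherwise specified, only those observed data from the patients will be used in the statistical analyses, ie, no estimation of missing data".

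Totals, subscale scores and their changes from baseline are summarised descriptively at each time point. The data are also listed, and individual plots are provided.

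**The concern.** A sum over the answered items gives the same number as scoring every unanswered item 0. On this scale 0 is a substantive answer: the problem is absent. An incomplete form therefore gives a total that is too low, or at best unchanged, for reasons unrelated to the child's behaviour. The table shows it beside complete forms without distinction.

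The SAP handles its other summed scales differently:

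- MD-CRS (4.3.5.1) is rescaled through the index.
- UHDRS (6.5.3.1) replaces missing items by the average of the rest, up to 25% missing.
- PedsQL (6.5.5.1) divides by the number of items answered.
- ESRS I and II (8.13.1, 8.13.2) replace missing items by an average.
- ESS (8.12) is invalid with any blank.
- The CBCL Competence Scale (8.11.1) allows one missing item in the Activities or Social subscale, where "the mean of the other items of that subscale is substituted for that item". Otherwise it does not score the subscale, and it then gives no total.

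Only the Syndrome total combines a wide allowance for missing items with no stated adjustment. CBCL is a named safety variable (Section 1.3). Descriptive safety tables tend to be read at face value, so a scoring artefact in the change from baseline could hide a behavioural signal or create one. The scale is given at eight time points, so the problem can recur at each.

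**Working it through.** The SAP states no figure to reproduce, so the check is of what the scoring rule does.

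**Inputs from the SAP**

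- Entries in Table 12: 13 + 8 + 11 + 11 + 15 + 17 + 10 + 18 (the eight subscales) + 17 (Other Problems) = 120. This agrees with 113 numbered questions, because item 56 is split into a to h (113 + 7 = 120).
- Items subject to the missing-item rules: 120 − 2 (56h and 113) = 118.
- Blanks allowed before the total is withheld: 20.

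**Assumptions (not in the SAP)**

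- Mean item score 0.2 to 0.5.
- Blank rate per item m of 1% to 3%, independent across items and unrelated to the item's score.

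**1. Loss at the limit.** Share of the form blank: 20/118 = 16.9%. Understatement = blanks × mean item score:

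- 20 × 0.2 = 4 points
- 20 × 0.5 = 10 points
- absolute ceiling: 20 × 2 = 40 points, out of a maximum of 2 × 118 = 236

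**2. Average loss at ordinary blank rates.** Expected blanks = 118 × m, which is 1.2 at 1% and 3.5 at 3%. Expected understatement = 118 × m × mean item score:

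- smallest: 118 × 0.01 × 0.2 = 0.24 points
- largest: 118 × 0.03 × 0.5 = 1.77 points

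At these rates more than 99.9% of forms stay within the 20-item limit. The 4 to 10 point loss therefore describes an exceptional form, not the typical one.

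**3. How many totals are lowered.** The chance of at least one blank is 1 − (1 − m)^118, which is 69% at 1% and 97% at 3%. A blank on an item whose true answer is 0 changes nothing. With a mean item score of 0.2 to 0.5, at most 20% to 50% of items are non-zero. The share of totals lowered is thus at most 1 − (1 − m × p)^118 with p = 0.2 to 0.5:

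- m = 1%: 21% to 45%
- m = 3%: 51% to 83%

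**4. Effect on change from baseline.** Take a child with no true change and a mean item score of 0.3, so the complete total is 0.3 × 118 = 35.4. With 20 blanks the sum is 0.3 × 98 = 29.4.

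- Blanks at follow-up only: 29.4 − 35.4 = −6.0 (false improvement).
- Blanks at baseline only: 35.4 − 29.4 = +6.0 (false worsening).
- Same items blank at both visits: the errors cancel.
- Prorated: 29.4 × 118/98 = 35.4, so the change is 0 in the first two cases.

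**5. Cost of the one-blank subscale rule.** The chance that a k-item subscale is not scored is 1 − (1 − m)^k. At m = 1%:

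- 13 items (Anxious/Depressed): 12.2%
- 18 items (Aggressive Behavior): 16.5%
- change from baseline in the 13-item subscale, which needs two complete forms: 1 − 0.99^26 = 23.0%

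**The case against.** **The SAP never says that a blank is scored 0.** True. It follows from the sum rule and the no-estimation default. If a different total was intended, for example none when any item is blank, the text does not say so, and that would also need correcting.

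**The rule does not favour one direction.** This stands. A reader might infer that incomplete forms look like behavioural improvement. Only the single form's total has a known direction. Change can be biased either way, and equal blank rates at both visits give an expected bias of zero. Bias between arms needs missingness that differs by arm, and nothing in the SAP of this double-blind trial suggests that.

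**The total and subscale rules do not contradict each other.** This also stands. They can be carried out in sequence, and different tolerances for a 118-item total and an 8- to 18-item subscale are a scoring choice. Zero tolerance appears elsewhere too: in the ESS and in the School subscale of the Competence Scale.

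**The depression subscales are not singled out.** Correct. The one-blank rule applies to every subscale and costs the longer ones more.

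**The consequence is limited.** The CBCL output is descriptive, with no test. Listings and individual plots remain available. Adverse events, and the C-SSRS from age 12, also capture mood and behaviour. This lowers the priority of the point but does not make the total right.

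**Conclusion.** The point holds for the total score. As written, Section 8.11.2 gives a Syndrome total that each blank can lower and never raise, with up to 17% of the form missing. The loss is 4 to 10 points at the 20-item limit and about 0.2 to 1.8 points on average at blank rates of 1% to 3%. All these sizes rest on assumed item means and blank rates, because the SAP gives neither. The limit case and the average case should not be combined: forms with 20 blanks practically do not arise at 1% to 3%.

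Three stronger conclusions are not supported. The SAP does not show a systematic drift towards improvement or a bias between arms. The 69% to 97% of forms with at least one blank is not the share of totals biased downward; that share is at most 21% to 45% at a 1% blank rate and 51% to 83% at 3%. The subscale rule loses patients, but it is a strict choice and not an error.

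This is a cheap improvement to a descriptive safety summary. It does not affect the efficacy conclusions.

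**What to change.** Add to Section 8.11.2:

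- When 1 to 20 items other than 56h and 113 are missing, prorate the total: sum of the answered items among the 118, times 118, divided by the number answered, plus 56h and 113 if they were given.
- Keep the total missing when more than 20 of the 118 are blank.
- Report the number of incomplete forms and of unscored subscales by arm and visit.

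Because the adjustment works on the whole form, it also covers blanks in an unscored subscale and in Other Problems, which lies outside the eight subscales. The one-blank subscale rule may stay; the reported counts will show what it costs.

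The cost is a few lines of SAP text and a small change to the scoring program. The downside is light proration, which assumes that unanswered items would on average have scored like the answered ones. That is a milder assumption than scoring them all 0.
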